2. STUDY SCHEDULES

Table 1: Study Schedule for Phase 1 Expansion

NOTE: Evaluations on D1 of a cycle should be performed within 24 hours prior to dosing, unless otherwise noted. Procedures already performed during the screening period within 72 hours prior to dosing do not need to be repeated on C1D1. The EOT visit must be performed 0-7 days after the decision is made to discontinue study treatment (for patients who discontinue at a planned study visit, that visit may be considered the EOT visit if all assessments required at EOT are performed).

	Screening Period (Within 28 Days Prior to First Dose)	Treatment Period (1 cycle = 21 days)				Safety Follow-up		Survival Follow-up Period	Notes
		Cycle 1			Cycles ≥2	End of Tx (+0-7 days)	30 (±3) days After Last		
		Day 1	Day 4 (±1d)	Day 8 (±3d)	Day 15 (±3d)				
Written informed consent	X								
Review eligibility criteria	X	X							
Demographics/medical history	X								
Physical examination	X	X			X	X	X		
Review of pre-existing signs and symptoms	X	X							
Tumor tissue sample collection		(X)							At any time during the study; tumor tissue collection is mandatory if tissue is available.
Vital signs	X	X			X	X	X		Heart rate, blood pressure, body temperature, and respiration rate.
Height and Weight	X	X			X	X	X		Height at screening only.
Ophthalmological examination	X				(X)	X	X		At screening and 4-6 weeks after first dose; additional on-study evaluation as needed due to local requirements, physician judgment, and/or symptoms or signs of mineral deposits.
Neurological examination	X	(X)			(X)	X	X		As clinically indicated after screening, using same methods used at screening.
Neurological examination as part of RANO (Group 5)	X	(X)			(X)	X	X		For patients with primary CNS tumors, a neurological examination must be performed within 1 week of the date of the Gd-MRI performed at screening and as part of RANO response assessment.

	Screening Period (Within 28 Days Prior to First Dose)	Treatment Period (1 cycle = 21 days)					Safety Follow-up		Survival Follow-up Period	Notes	
		Cycle 1				Cycles ≥2	End of Tx (+0-7 days)	30 (±3) days After Last			
		Day 1	Day 4 (±1d)	Day 8 (±3d)	Day 15 (±3d)	Day 1 (±3d)					
ECOG performance status	X	X				X	X	X			
12-Lead Electrocardiogram	X	X				X	X	X		At screening and 2 hours (±15 minutes) after dosing on D1 of each cycle.	
Hematology and coagulation	X	X		X	X	X	X	X		Within 24 hours prior to treatment on D1 of each cycle, any time on C1D8 and C1D15, and as clinically indicated.	
Chemistry (Serum or plasma)	X	X	(X)	X	X	X	X	X		Within 24 hours prior to treatment on D1 of each cycle, any time on C1D8 and C1D15, and as clinically indicated. Additional collection for phosphorus only at C1D4.	
Urinalysis (Urine dipstick)	X	X				X	X	X			
Pregnancy test	X	X				X	X	X		Serum pregnancy test required for WOCBP at screening and end of treatment; serum or urine pregnancy test required at all other timepoints.	
Blood PK Sampling (Required)						X				Blood samples (1 mL) collected C2D1 pre-dose and at 1h and 3h (±30 min) post-dose. Additional samples collected pre-dose on C3D1 and C4D1.	
Blood PK Sampling (Optional)		Blood samples (minimum 1 mL) collected any day if needed, prior to dose and 1, 2, 3, 4, 6, and 24 hours post-dose.									See also Section 9.13.1
Blood and CSF PK Sampling (Blood, CSF; Optional) (Group 5 only)						(X)				Blood and CSF samples (minimum 1 mL of whole blood and CSF each) collected 2-4 hours after dose on C2D1. See also Section 9.13.1	
ctDNA blood samples	X						(X)			Minimum of 20 mL whole blood at screening (mandatory) and EOT (optional).	

	Screening Period (Within 28 Days Prior to First Dose)	Treatment Period (1 cycle = 21 days)				Safety Follow-up		Survival Follow-up Period	Notes
		Cycle 1			Cycles ≥2	End of Tx (+0-7 days)	30 (±3) days After Last		
		Day 1	Day 4 (±1d)	Day 8 (±3d)	Day 15 (±3d)				
CCI									
Prior & concomitant medications, AE assessments	X	—————→				X	X		Collect from the time informed consent (ICF) is signed through 30 days after administration of the last dose of TAS-120.
Tumor assessments / scans	X					X	X	(X)	
Perform the same tumor assessments/scans obtained at screening at the end of every 2 cycles (up to +2 weeks) up to Cycle 4. Thereafter tumor assessments may be performed every 3 cycles (± 7 days), or as clinically indicated, until radiologic disease progression or initiation of new anticancer therapy (whichever occurs first).
 
At EOT, tumor assessment must be performed if the prior scan was performed ≥9 weeks prior to discontinuation of treatment if the patient discontinued for reasons other than radiologic disease progression. See also Section 9.17.
 
After EOT, patients who discontinued for reasons other than radiologic disease progression should continue to receive tumor assessments every 3 cycles (± 7 days), or as clinically indicated, until radiologic disease progression or initiation of new anticancer therapy (whichever occurs first).

	Screening Period (Within 28 Days Prior to First Dose)	Treatment Period (1 cycle = 21 days)				Safety Follow-up		Survival Follow-up Period	Notes
		Cycle 1			Cycles ≥ 2	End of Tx (+0-7 days)	30 (± 3) days After Last		
		Day 1	Day 4 ($\pm 1d$)	Day 8 ($\pm 3d$)	Day 15 ($\pm 3d$)				
Survival status								X	After discontinuation of treatment, survival follow-up in a given group should occur every 3 months (± 2 weeks) for up to 12 months after last patient enrolled in that group.
TAS-120 Dosing		—————→							Patients are required to fast for at least 2 hours before and 1 hour after each administration of TAS-120; patients are permitted to drink water during this period. TAS-120 should be administered in the morning or evening, at the same time (if possible) each day. See Section 8.1.1.

Table 2: Study Schedule for Phase 2

NOTE: Evaluations on D1 of a cycle should be performed within 24 hours prior to dosing, unless otherwise noted. Procedures already performed during the screening period within 72 hours prior to dosing do not need to be repeated on C1D1. The EOT visit must be performed 0-7 days after the decision is made to discontinue study treatment (for patients who discontinue at a planned study visit, that visit may be considered the EOT visit if all assessments required at EOT are performed).

	Pre-Screening	Screening Period (Within 28 Days Prior to First Dose)	Treatment Period (1 cycle = 21 days)				Safety Follow-up		Survival Follow-up Period	Notes	
			Cycle 1				Cycles ≥2	End of Tx (+0-7 days)			30 (±3) days After Last
			Day 1	Day 4 (±1d)	Day 8 (±3d)	Day 15 (±3d)	Day 1 (±3d)				
Written informed consent	(X)	X							Pre-screening ICF if required for determination of eligibility.		
Tumor tissue testing of FGFR2 gene fusions / rearrangements			Tumor tissue may be tested by central laboratory during pre-screening. If previously tested by central laboratory, it is requested that tumor tissue be provided if available. In cases where local laboratory testing is used to determine eligibility, it is requested that tumor tissue be provided, if available from either archival samples or fresh tumor biopsy.								
Review eligibility criteria		X	X								
Demographics/medical history		X									
Review of pre-existing signs and symptoms		X	X								
Physical examination		X	X			X	X	X	Within 24 hours prior to dosing on D1 of each cycle.		
Vital signs		X	X			X	X	X	Heart rate, blood pressure, body temperature, and respiration rate.		
Height and Weight		X	X			X	X	X	Height at screening only.		
Ophthalmological examination		X				(X)	X	X	At screening and 4-6 weeks after first dose; additional on-study evaluation as needed due to local requirements, physician judgment, and/or symptoms or signs of mineral deposits.		
Neurological examination		X	(X)			(X)	X	X	As clinically indicated after screening, using same methods used at screening.		
ECOG performance status		X	X			X	X	X	Within 24 hours prior to dosing on D1 of each cycle.		
12-Lead Electrocardiogram		X	X			X	X	X	At screening and 2 hours (±15 minutes) after dosing on D1 of each cycle.		

	Pre-Screening	Screening Period (Within 28 Days Prior to First Dose)	Treatment Period (1 cycle = 21 days)					Safety Follow-up		Survival Follow-up Period	Notes
			Cycle 1				Cycles ≥2	End of Tx (+0-7 days)	30 (±3) days After Last		
			1	Day 4 (±1d)		8 (±3d)	15 (±3d)				
Hematology and coagulation		X	X		X	X	X	X		Within 24 hours prior to treatment on D1 of each cycle, any time on C1D8 and C1D15, and as clinically indicated.	
Chemistry (Serum or plasma)		X	X	(X)	X	X	X	X		Within 24 hours prior to treatment on D1 of each cycle, any time on C1D8 and C1D15, and as clinically indicated. Additional collection for phosphorus only at C1D4.	
Urinalysis (Urine dipstick)		X	X			X	X	X			
Pregnancy test		X	X			X	X	X		Serum pregnancy test required for WOCBP at screening and end of treatment; serum or urine pregnancy test required at all other timepoints.	
Blood PK Sampling (Required)						X				Blood samples (1 mL) collected C2D1 pre-dose and at 1h and 3h (±30 min) post-dose. Additional samples collected pre-dose on C3D1 and C4D1.	
ctDNA blood samples		X					(X)			Minimum of 20 mL whole blood at screening (mandatory) and EOT (optional).	
CCI											
Prior & concomitant medications, AE assessments	X	X	—————→				X	X			Collect from the time main informed consent is signed through 30 days after administration of the last dose of TAS-120 or until the start of new anticancer therapy, whichever is earlier. AEs directly associated with a pre-screening procedure should be reported as described in Section 11.1.

	Pre-Screening	Screening Period (Within 28 Days Prior to First Dose)	Treatment Period (1 cycle = 21 days)					Safety Follow-up		Survival Follow-up Period	Notes
			Cycle 1				Cycles ≥ 2	End of Tx (+0-7 days)	30 (± 3) days After Last		
			1	Day 4 ($\pm 1d$)		8 ($\pm 3d$)	15 ($\pm 3d$)				
PRO (EQ-5D and EORTC QLQ-C30)		X					X			Evaluated at screening and as close as possible to the tumor assessment schedule: at the end of every 2 cycles (up to +2 weeks) through Cycle 4 and every 3 cycles (± 7 days) thereafter until disease progression or initiation of new anticancer therapy (whichever is first).	
Tumor assessments / scans		X					X		(X)	
Same tumor assessments/scans obtained at screening at the end of every 2 cycles (up to +2 weeks) up to Cycle 4. Thereafter tumor assessments may be performed every 3 cycles (± 7 days), or as clinically indicated, until radiologic PD or initiation of new anticancer therapy (whichever occurs first).
 
At EOT, tumor assessment must be performed if the prior scan was performed ≥ 9 weeks prior to discontinuation of treatment if the patient discontinued for reasons other than radiologic disease progression. See also Section 9.17.
 
After EOT, patients who discontinued for reasons other than radiologic disease progression should continue to receive tumor assessments every 3 cycles (± 7 days), or as clinically indicated, until radiologic disease progression or initiation of new anticancer therapy (whichever occurs first).
	

	Pre-Screening	Screening Period (Within 28 Days Prior to First Dose)	Treatment Period (1 cycle = 21 days)				Safety Follow-up		Survival Follow-up Period	Notes
			Cycle 1			Cycles ≥ 2	End of Tx (+0-7 days)	30 (± 3) days After Last		
			Day 1	Day 4 ($\pm 1d$)	Day 8 ($\pm 3d$)	Day 15 ($\pm 3d$)				
Survival status								X	After discontinuation of treatment, survival follow-up should occur every 3 months (± 2 weeks) for up to 18 months after last patient enrolled in the Phase 2 portion of the study.	
TAS-120 Dosing			—————→							Patients are required to fast for ≥ 2 hours before and 1 hour after each administration of TAS-120; patients are permitted to drink water. TAS-120 should be administered in the morning or evening, at the same time (if possible) each day. See Section 8.1.1.

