9.17. Tumor Assessments/Scans

9.17.1. Tumor Assessment for Advanced Solid Tumors

Tumor assessments/imaging studies of the chest, abdomen, and pelvis (as clinically indicated) must be obtained at each time point listed below for all patients with solid tumors.

- Screening within 28 days prior to Day 1 of Cycle 1. Computed tomography scans obtained prior to the signed ICF may be used as the screening scan if they were obtained within 28 days of the first dose of TAS-120.
- At the end of every 2 cycles (up to +2 weeks), up to Cycle 4.
- Following Cycle 4, at least after every 3 cycles (\pm 7 days) or as clinically indicated, until documented progression (including after end of treatment if the patient discontinues for reasons other than radiologic disease progression).
- At end of treatment (+0-7 days), a CT scan must be performed if the prior scan was performed \geq 9 weeks prior to discontinuation of TAS-120 treatment if the patient discontinued for reasons other than radiologic disease progression.

On-site tumor assessments will be performed by the investigator/local radiologist according to RECIST guidelines (version 1.1, 2009). Results of these assessments, including response for target and non-target lesions and appearance of new lesions, will be the basis for the continuation or discontinuation of TAS-120. Response definitions are provided in [Section 10](#), Efficacy Assessment Criteria.

If the investigator determines that a patient has developed clinical progression manifested by symptomatic deterioration but not supported by radiologic evidence of progression, the patient should stop treatment. Symptoms of clinical progression must be documented in the patient's source documents and must be reported as AEs. Every effort should be made to document objective progression even after discontinuation of treatment.

The same method of assessment and the same technique must be used to characterize each identified and reported lesion at Screening, throughout the study, and during the follow-up period.

On-site tumor assessments will be conducted. Tumor assessment scans from patients with iCCA treated at 16, 20 and 24 mg QD and patients with primary brain tumors may also be prospectively or retrospectively collected and forwarded to the core imaging laboratory.

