12.2.2. Efficacy Analysis

Tumor assessments will be performed as per [Section 9.17](#), Tumor Assessments/Scans. For the Phase 1 Expansion, the primary endpoint is ORR (and EPR for primary CNS tumors), and secondary endpoints are DCR, DOR, PFS, OS.

For Phase 2, the primary endpoint is ORR and the secondary endpoints are DOR, DCR, PFS, PROs and OS (response evaluations based on independent review of images by the Core Imaging Laboratory). In addition, sensitivity analyses for some key efficacy endpoints (notably ORR and PFS) will be performed based on assessments by the investigator or local radiologist.

Response assessments will be made based on RECIST guidelines (version 1.1, 2009) for solid tumors (see [Section 10.1](#), Efficacy Assessment for Solid Tumors) or RANO for brain tumors (see [Section 10.2](#)).

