12.2.2.4. Progression-free Survival

Progression-free survival (PFS) is defined as the time from the day of the first dose to the date of first objectively documented disease progression or death (any cause), whichever occurs first. Patients who die without a reported disease progression will be considered to have progressed on the date of their death. Patients who did not progress or die will be censored on the date of their last tumor assessment. Patients who did not have any on-study assessments and did not die will be censored on the first dosing date. Patients who started any subsequent anti-cancer therapy without a prior reported progression will be censored at the last tumor assessment prior to initiation of the subsequent anti-cancer therapy. Early progression rate (EPR) for the GBM or Grade III glioma cohort will be assessed as the progression-free rate at the end of Cycle 2.

Progression-free survival will also be analyzed as a time-to-event endpoint with the median (Kaplan-Meier estimate) and associated 95% CI (Brookmeyer-Crowley methodology) reported, along with the Kaplan-Meier estimates for PFS rates at 3, 6, 9 and 12 months and associated 95% CIs (log-log transformation methodology of Kalbfleisch-Prentice).

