# **6.4.2.1.** Sensitivity Analyses

The following sensitivity analyses will be performed on the key efficacy endpoints as follows:

- Primary efficacy endpoint (ORR) based on the Per-protocol Analysis Set using a similar analysis method as the primary analysis
- ORR and PFS based on assessments by the investigator or local radiologist on the Efficacy Population

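### Phase 2 scans in effect stop at the site's call of progression while DOR and PFS are read centrally, so central-read DOR and PFS may be biased upward by an amount the plan does not measure

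*Protocol*

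**What the plan says.** **When scanning ends.** Protocol Section 2, Table 2 schedules Phase 2 scans until radiologic progression or new anticancer therapy. After the end of treatment, "patients who discontinued for reasons other than radiologic disease progression should continue to receive tumor assessments every 3 cycles". The table does not say whose reading of progression counts.

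**Who decides.** Protocol 9.17.1 has the investigator or local radiologist read the scans on site, and those results "will be the basis for the continuation or discontinuation of TAS-120".

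**Who reads the endpoint.** For Phase 2, Protocol 12.2.2 lists ORR, DOR, DCR, PFS, PROs and OS with "response evaluations based on independent review of images by the Core Imaging Laboratory". DOR is the key secondary objective (Protocol 6.3).

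**Censoring.** Protocol 12.2.2.4: "Patients who did not progress or die will be censored on the date of their last tumor assessment". Protocol 12.2.2.3 treats DOR in the same way. Row 6 of Table 6 in the Phase 2 SAP censors a patient who starts new therapy before progression at the last scan before that therapy. Rows 4 and 5 cover discontinuation for reasons other than progression or death. No row is written for progression at the site without central progression.

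**Other analyses planned.** Phase 2 SAP 3.2.2 calculates ORR, DOR, DCR and PFS by both central and investigator assessment. The sensitivity list in 6.4.2.1 names "ORR and PFS based on assessments by the investigator or local radiologist on the Efficacy Population"; DOR is not in that list.

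**The concern.** Read together, these provisions mean that the site's call of progression normally ends treatment and scheduled scanning. If the central reader does not call progression on that scan, there is no later scheduled scan on which to do so. Unless the patient dies in a way that counts as an event, the central-read record ends in censoring on the day a radiologist judged that the tumor had progressed.

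Kaplan-Meier estimation takes censored patients to have the same future risk as those still under observation. Here the censoring is triggered by a judgment about the outcome itself. If the discordant patients are nearer progression than average, the central-read curves sit too high.

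Death is only a partial backstop. Rows 6 and 7 of Table 6 censor deaths after new therapy or after missed assessments, and the text of footnote a limits events to 21 days after the last dose.

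What is at stake is the durability evidence beside the response rate in a single-arm study. The SAP revision history ties the timing of the final analysis to follow-up of responders for the NDA submission.

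**Working it through.** **The plan's own figure.** The readable text gives no target, event count or power for DOR or PFS. The one Phase 2 efficacy figure that can be checked is the ORR rule of at least 17 responders in 100 (Phase 2 SAP 6.4.1). The Clopper-Pearson 95% lower bound is 10.23% for 17/100 and 9.43% for 16/100, so the rule reproduces. It does not depend on the censoring discussed here.

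**Inputs**
- Scans at the end of Cycles 2 and 4, then every 3 cycles of 21 days (Protocol Table 2): weeks 6, 12, 21, 30, 39, 48. Twelve months is week 52.2, so the week-48 scan is the last one that counts.
- Assumed: exponential progression with a 9-month (39.13-week) median, so λ = ln 2 / 39.13 = 0.01771 per week.
- Assumed: a fraction q of site progressions, 10% to 30%, is not called centrally on the same scan.
- Deaths and the data cut-off are left out.

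**Interval probabilities.** h = 1 − exp(−λ × gap). For a 6-week gap, h = 0.1008; for a 9-week gap, h = 0.1474.

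**Site progression counted as an event.** S(48) = exp(−0.01771 × 48) = 0.427, whatever q is.

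**As planned.** Discordant patients are censored at the site-progression scan, so each Kaplan-Meier factor is 1 − (1 − q)h:

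Plan = [1 − (1 − q) × 0.1008]² × [1 − (1 − q) × 0.1474]⁴

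At q = 20%: 0.9193² × 0.8821⁴ = 0.512.

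**Scans continued, all discordant patients truly progressing** (central progression called at the next scan). At 12 months the only difference from S(48) is the discordant patients first called by the site at week 48. With S(39) = 0.501:

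S(48) + q × [S(39) − S(48)]

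At q = 20%: 0.427 + 0.2 × 0.0739 = 0.442.

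**Scans continued, half truly progressing**, the other half carrying ordinary risk from that scan onward:

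S(48) + (q/2) × [S(39) − S(48)] + (q/2) × S(48) × Σ(exp(λ × gap) − 1)

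The sum over the six gaps is 0.9155, and 0.4273 × 0.9155 = 0.391. At q = 20%: 0.427 + 0.1 × 0.0739 + 0.1 × 0.391 = 0.474.

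**12-month PFS**

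| q | As planned | Continued, all progressing | Excess (points) | Continued, half progressing | Excess (points) | Site progression as event |
|---|---|---|---|---|---|---|
| 0% | 42.7% | 42.7% | 0 | 42.7% | 0 | 42.7% |
| 10% | 46.8% | 43.5% | 3.3 | 45.1% | 1.7 | 42.7% |
| 20% | 51.2% | 44.2% | 7.0 | 47.4% | 3.8 | 42.7% |
| 30% | 55.9% | 44.9% | 10.9 | 49.7% | 6.2 | 42.7% |

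A simulation of 200,000 patients on the same grid agrees. At q = 20% it gives 51.0% as planned against 44.1% with continued scanning, and interpolated medians of 11.4 against 9.4 months.

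The same mechanism acts on DOR among central-read responders. It was not sized separately.

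**The case against.** **Investigator-read DOR and PFS are already planned.** This is the strongest point. SAP 3.2.2 plans both, and neither has this censoring, because scans stop on the investigator's own call. In the model above central progression never precedes site progression, so counting site progression as an event is the same as investigator-read PFS. If central calls may also come one scan early (assumed 20% late and 20% early), 12-month PFS is 42.8% in truth, 42.6% by investigator, 41.3% with site progression added as an event, and 49.8% as planned. For PFS, then, the supplementary estimate adds little beyond the investigator read. For DOR it adds more: investigator DOR changes the responder set and the response dates, so a gap from central DOR cannot be put down to censoring. Neither planned analysis counts the discordant patients.

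**The SAP does have censoring rules.** It does, and it cites FDA guidance for them. A reader might infer that these patients have no rule at all. They are covered by the general rules in Protocol 12.2.2.3 and 12.2.2.4 and by row 6. The issue is that the rule which applies is likely to be informative.

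**Site progression need not end scanning at once.** This is fair. Protocol 7.3.1 lets treatment continue by agreement with the sponsor, and 10.1.3.1.1 carries equivocal findings to the next scan. Central confirmation could also be arranged in the Imaging Manual, which is not available here. A reader might infer purely retrospective central reading from the statement in 9.17.1 that scans "may also be prospectively or retrospectively collected and forwarded to the core imaging laboratory". That sentence concerns iCCA patients at 16, 20 and 24 mg and brain tumors, so it is weak evidence about Phase 2.

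**DOR and PFS are descriptive.** This is true, and it limits the consequence.

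**Conclusion.** The mechanism follows from the documents, and any bias would be upward wherever patients with site but not central progression are nearer progression than average. A reader might conclude that central-read DOR and PFS are inflated. The documents do not support that as a fact, because they give no discordance rate and the bias is zero if discordance is zero.

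Under the stated assumptions (10% to 30% discordance, a 9-month median, no deaths), 12-month PFS is about 3 to 11 points too high if every discordant patient is truly progressing. That is near a worst case. If half are, the excess is about 2 to 6 points. Primary ORR and its 17-of-100 rule are largely unaffected. The planned investigator reads show part of the gap, but they do not isolate it, least of all for DOR.

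**What to change.** In Phase 2 SAP 6.4.2.1:

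1. Report the number of patients with investigator-assessed radiologic progression but no central progression.
2. Add one supplementary analysis of DOR, among central-read responders, and of PFS. In it such a patient counts as an event on the date of the scan on which the investigator called progression, including where new therapy started afterwards.
3. Show these estimates beside the central-read ones.

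The cost is one SAP paragraph and a rerun of the existing Kaplan-Meier programs with a second event flag. Both reads are already planned, so no scans or readers are added. The downside is a somewhat conservative, less favourable companion figure: in the table above it falls below the continued-scanning value by 0.8 to 2.2 points if all discordant patients are progressing (43.5 − 42.7 and 44.9 − 42.7) and by 2.4 to 7.0 points if half are (45.1 − 42.7 and 49.7 − 42.7). In the scenarios calculated here, with central progression never ahead of the site's call, the two figures bracket the value that continued scanning would have given.
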